AST	Aspartate aminotransferase		
BID	Twice daily (or 2 times a day)		
BMI	Body mass index		
bpm	Beats per minute		
BUN	Blood urea nitrogen		
CBP	Childbearing potential		
CFR	Code of Federal Regulations		
CIOMS	Council for International Organizations of Medical Science		
CMH	Cochran-Mantel-Haenszel		
COVID-19	Coronavirus disease 2019		
CPK	Creatine phosphokinase		
CRF	Case report form		
CRO	Contract research organization		
C-SSRS	Columbia-Suicide Severity Rating Scale		
DNA	Deoxyribonucleic acid		
ECG	Electrocardiogram		
eCRF	Electronic case report form		
eICF	Electronic informed consent form		
EDE	Eating Disorder Examination		
EDE-Q	Eating Disorder Examination Questionnaire		
EDE-Q7	Eating Disorder Examination Questionnaire - 7-Item Version		
ESAM	Events subject to additional monitoring		
ET	Early termination		
CCI			
FDA	Food and Drug Administration		
GCP	Good Clinical Practice		
GGT	Gamma glutamyl transferase		
HAM-A	Hamilton Anxiety Rating Scale		
HbA1c	Glycosylated hemoglobin		
hCG	Human chorionic gonadotropin		
HDL	High-density lipoprotein		
IB	Investigator's Brochure		
ICH	International Council for Harmonisation		
ICMJE	International Committee of Medical Journal Editors		
ID	Identifier		
IMP	Investigational medicinal product		
INR	International normalized ratio		
IRB	Institutional review board		
IRE	Immediately reportable event		

Abbreviation	Definition
K ₂ EDTA	Dipotassium ethylenediaminetetraacetic acid
LDH	Lactic dehydrogenase
LOE	Lack of efficacy
MADRS	Montgomery-Asberg Depression Rating Scale
MAR	Missing at random
MCH	Mean corpuscular hemoglobin
MCS	Mental Component Summary score
MedDRA	Medical Dictionary for Regulatory Activities
MHI	Medication handling irregularity
MMRM	Mixed-effect model repeated measures
MNAR	Missing not at random
OC	Observed cases
OPDC	Otsuka Pharmaceutical Development & Commercialization, Inc
PCS	Physical Component Summary score
PK	Pharmacokinetic
PQC	Product quality complaint
PT	Prothrombin time
QTc	Corrected QT interval
QTcF	QT interval corrected for heart rate using Fridericia's formula
RBC	Red blood cell count
RDW	Red cell distribution width
RNA	Ribonucleic acid
SAE	Serious adverse event
SAP	Statistical analysis plan
SCID-5-CT	Structured Clinical Interview for DSM-5 Disorders, Clinical Trials
	Version
SF-36v2	36-item Short-Form Health Survey Version 2
SMWQ	Study Medication Withdrawal Questionnaire
T_4	Thyroxine
TDD	Total daily dose
TEAE	Treatment-emergent adverse event
TSH	Thyroid stimulating hormone
ULN	Upper limit of normal
WBC	White blood cell count

1 Protocol Summary

1.1 Synopsis

Name of Sponsor: Otsuka Pharmaceutical Development & Commercialization, Inc.

Name of Investigational Medicinal Product: Centanafadine (EB-1020)

Protocol No.: 405-201-00056

IND No.: 155,243

Protocol Title: A Phase 2, Multicenter, Randomized, Double-blind, Placebo-controlled Trial to Assess the Efficacy, Safety, and Tolerability of Centanafadine Sustained-release Tablets After Oral Administration in Adult Subjects with Binge Eating Disorder

Protocol Lay Person Short Title: A Trial of Centanafadine Efficacy, Safety, and Tolerability in Adult Subjects with Binge Eating Disorder

Clinical Phase: 2

Treatment/Indication: Binge eating disorder (BED)

Objectives and Endpoints:

Objectives	Endpoints
Primary: To assess the efficacy of 2 doses of centanafadine SR (200 and 400 mg TDD) compared with placebo in adults with moderate to severe BED.	Primary Efficacy: Change from baseline in binge eating days per week at Weeks 7-8, having binge eating day defined as a day with at least one binge eating episode Key Secondary Efficacy: Change from baseline in CGI-S score at Week 8
	Other Efficacy: Change from baseline in CGI-S score at Weeks 1, 2, 3, 4, and 6 CGI-C score
	Change from baseline in Y-BOCS-BE score
	Proportion of subjects with four-week cessation from binging at Week 8/ET
	Change from baseline in number of binge episodes per week
	Change from baseline in PGI-S score
	PGI-C score
	Change from baseline in SF-36v2 PCS and MCS scores
	Change from baseline in EDE-Q7 total score

Objectives	Endpoints
Secondary:	Safety: AEs (including AESIs [rash],
To assess the safety and tolerability of	abuse-related AEs, and AEs involving MHIs),
centanafadine SR tablets administered daily (200	clinical laboratory tests (hematology, serum
and 400 mg TDD) in the treatment of subjects	chemistry [including change from baseline in
with BED.	total cholesterol and triglycerides], and
	urinalysis), vital sign measurements (including
	change from baseline in body weight and
	percent change from baseline in body weight),
	12-lead ECGs, SMWQ, HAM-A, MADRS, and
	C-SSRS

AE = adverse event; AESI = adverse event of special interest; CGI-C = Clinical Global Impression - Change; CGI-S = Clinical Global Impression - Severity; C-SSRS = Columbia-Suicide Severity Rating Scale; ECG = electrocardiogram; EDE-Q7 = Eating Disorder Examination Questionnaire - 7-Item Version; ET = early termination; HAM-A = Hamilton Anxiety Rating Scale; MADRS = Montgomery-Asberg Depression Rating Scale; MCS = Mental Component Summary score; MHI = medication handling irregularity; PCS = Physical Component Summary score; PGI-C = Patient Global Impression - Change; PGI-S = Patient Global Impression - Severity; SF-36v2 = 36-item Short-Form Health Survey Version 2; SMWQ = Study Medication Withdrawal Questionnaire; TDD = total daily dose; Y-BOCS-BE = Yale-Brown Obsessive-Compulsive Scale Modified for Binge Eating.

Trial Design: This will be a phase 2, multicenter, randomized, double-blind, placebo-controlled trial to assess the efficacy, safety, and tolerability of centanafadine SR tablets for the treatment of adult subjects with BED. The trial will consist of a 28-day screening period that includes completion of a binge eating diary for at least 14 days, a baseline visit, an 8-week (56-day) double-blind treatment period, and a 7-day safety follow-up period. All baseline assessments will be conducted prior to first dose of IMP.

Trial Population: Approximately 228 adult subjects with BED are anticipated to be screened with the expectation that approximately 126 subjects will be randomized (42 subjects per treatment arm).

Key Inclusion/Exclusion Criteria: Subjects will be 18 to 65 years of age (inclusive), with a primary diagnosis of BED of at least moderate severity, with a history of at least 2 binge eating days per week for 6 months prior to screening and at least 3 binge eating days in each week during the previous 14 days of a subject's screening period as reviewed at baseline (minimum screening period is 2 weeks), a rating of 4 or higher on the Clinical Global Impression - Severity (CGI-S) at screening and baseline, and a BMI of 18 to 45 kg/m², inclusive. Subjects with a lifetime history or current diagnosis of bulimia nervosa or anorexia nervosa will be excluded.

[figure not shown]
Trial Site(s): This is a multicenter trial in the United States.

Investigational Medicinal Product(s), Dose, Dosage Regimen, Treatment Duration, Formulation, Mode of Administration: IMP consisting of high dose centanafadine (400 mg total daily dose [TDD]), low dose centanafadine (200 mg TDD), or placebo will

be administered orally as 100 mg sustained-release (SR) tablets or matching placebo taken twice daily, approximately 4 to 6 hours apart.

Trial Assessments:

Assessments for Efficacy: Binge eating diary, CGI-S, Clinical Global Impression - Change (CGI-C), Yale-Brown Obsessive-Compulsive Scale Modified for Binge Eating (Y-BOCS-BE), Eating Disorder Examination Questionnaire (EDE-Q), Eating Disorder Examination Questionnaire - 7-Item Version (EDE-Q7), Patient Global Impression - Severity (PGI-S), Patient Global Impression - Change (PGI-C), 36-item Short-Form Health Survey Version 2 (SF-36v2)

Assessments for Safety: AEs (including AESI evaluations [rash], abuse-related AEs, and AEs involving medication handling irregularities [MHIs]), clinical laboratory tests (hematology, serum chemistry [including total cholesterol and triglycerides], and urinalysis), physical examinations, vital sign measurements (including body weight), electrocardiograms (ECGs), and assessments of suicidality (Columbia-Suicide Severity Rating Scale [C-SSRS]), withdrawal (Study Medication Withdrawal Questionnaire [SMWQ]), anxiety (Hamilton Anxiety Rating Scale [HAM-A]), and depression (Montgomery-Asberg Depression Rating Scale [MADRS]).

Screening/Other: pregnancy test, urine drug screen/alcohol testing via breathalyzer, blood, or urine, and psychiatric evaluation

Data Monitoring Committee: No

Statistical Methods: Assuming a treatment difference of 1.1 points with a standard deviation of 1.7 in the mean change from baseline in binge eating days per week at Weeks 7-8 in either centanafadine dose group (high dose centanafadine or low dose centanafadine) compared to the placebo group (effect size = 0.65), a sample size of 114 evaluable subjects (38 in each treatment arm) will yield at least 80% power to detect the treatment effects at a 2-tailed significance level of 0.05. Approximately 126 subjects will be randomized (42 in each treatment arm) to ensure 114 evaluable subjects in the study. The primary efficacy analysis will be performed by fitting a mixed-effect model repeated measures (MMRM) analysis with an unstructured variance covariance structure, in which change from baseline in binge eating days per week at the scheduled visits will be the dependent variable based on the observed cases (OC) data set. The model will

include fixed effect terms for treatment, trial center, visit week, and an interaction term of treatment by visit week. The model will also include the interaction term of baseline values of binge eating days per week by visit week as covariates. The primary comparison between centanafadine groups and the placebo group at Weeks 7-8 will be estimated as the difference between Least Squares means utilizing the computing software SAS procedure PROC MIXED. If there is a convergence problem with the unstructured variance covariance matrix of the MMRM model, the following structures other than unstructured will be used in order of 1) heterogeneous toeplitz, 2) heterogeneous autoregressive of order 1, and 3) heterogeneous compound symmetry and the first (co)variance structure converging to the best fit will be used as the primary analysis. If a structured covariance has to be used, the "sandwich" estimator of the standard error of the fixed effects parameters will be used in order to deal with possible model misspecification of the covariance matrix.

[figure not shown]
Trial Duration:

The anticipated duration for each participant to complete the trial is up to 13 weeks, which will include the following periods:

- Screening period: up to 4 weeks (28 days)
- Double-blind treatment period: 8 weeks
- Follow-up period: 7 (+ 2) days

Overall, the trial duration from signing of the first informed consent form to the final subject assessment is expected to be approximately 10 months.

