9.1 Sample Size

Assuming a treatment difference of 1.1 points with a standard deviation of 1.7 in the mean change from baseline in binge eating days per week at Weeks 7-8 in either centanafadine dose group (high dose centanafadine or low dose centanafadine) compared to the placebo group (effect size = 0.65), a sample size of 114 evaluable subjects (38 in each treatment arm) will yield at least 80% power to detect the treatment effects at a 2-tailed significance level of 0.05. Approximately 126 subjects will be randomized to ensure 114 evaluable subjects in the study. The power and sample size were obtained using the PASS 14 (2015) statistical computing software.

9.2 **Datasets for Analysis**

The following datasets are defined for this trial:

[figure not shown]
- Randomized Analysis Set: comprises all subjects who were randomized in the double-blind treatment period. Subjects are considered randomized when they are assigned a treatment group at the baseline visit.
- Safety Analysis Set: comprises those randomized subjects in the double-blind treatment period who receive at least 1 dose of double-blind IMP. Subjects will only be excluded from this population if there is documented evidence (ie, numbers of drug dispensed are equal to numbers of drug returned, or no IMP dispensed at all) that the subject did not take IMP. If a subject is dispensed IMP and is lost to follow-up, he/she will be considered exposed.

• Efficacy Analysis Set: comprises all subjects in the Safety Analysis Set who have a baseline value and at least 1 valid post-randomization efficacy evaluation in the double-blind treatment period.

The core dataset for all efficacy analyses is the Efficacy Analysis Set. In order to handle missing data and restrictions imposed by different types of analyses (eg, change from baseline analysis), datasets derived from Efficacy Analysis Set will be used for the efficacy analysis.

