9.3 Handling of Missing Data for Primary and Key Secondary Endpoint Analysis

The mixed-effect model repeated measures (MMRM) assumes data are missing at random (MAR), which is a reasonable assumption in longitudinal clinical trials in the binge eating disorder population. However, the possibility of "missing not at random"

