The primary efficacy analysis will be performed by fitting an MMRM analysis with an unstructured variance covariance structure, in which change from baseline in binge eating days per week at the scheduled visits will be the dependent variable based on the OC data set. The model will include fixed effect terms for treatment, trial center, visit week, and an interaction term of treatment by visit week. The model will also include the interaction term of baseline values of binge eating days per week by visit week as covariates. The level of visit in the MMRM will include Week 1, Week 2, Week 3, Week 4, Week 6, and Week 8. The primary comparison between centanafadine groups and the placebo group at Weeks 7-8 will be estimated as the difference between Least Squares means utilizing the computing software SAS procedure PROC MIXED. If there is a convergence problem with the unstructured variance covariance matrix of the MMRM model, the following structures other than unstructured will be used in order of 1) heterogeneous toeplitz, 2) heterogeneous autoregressive of order 1, and 3) heterogeneous compound symmetry and the first (co)variance structure converging to the best fit will be used as the primary analysis. If a structured covariance has to be used, the "sandwich" estimator of the standard error of the fixed effects parameters will be used in order to deal with possible model misspecification of the covariance matrix. Details of this analysis will be provided in the SAP.

Within MMRM analysis, baseline is defined as the last available measurement prior to the first dose of IMP in the double-blind treatment period and small centers will be pooled as needed. The linear model assumptions will also be checked. Details will be provided in the SAP.

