8.2.3 Technical Computational Details for Primary Efficacy Analysis

8.2.3.1 Calculation of Binge Eating Days per Week

Binge eating day is defined as a day with at least one confirmed binge eating episode. Binge eating days weekly¹¹ is calculated as the number of confirmed binge eating days divided by the number of non-missing diary days and multiplied by 7 within specified trial day intervals for the mapped week in Table 5.2.-1. In addition, it is required to have non-missing diary data for at least 5 days in calculation of weekly binge eating days. If subjects have missing diary data for more than 2 days at a specific week prior to termination/completion, weekly binge eating days will be set as missing.

Binge eating days per week at Week 1, 2, 3 and 4 (scheduled visits) is equivalent to the calculated weekly binge eating days as specified above. Binge eating days per week for week 6 (scheduled visit) is average of binge eating days on the mapped Week 5 and binge eating days on the mapped Week 6. Similarly, binge eating days per week for week 8(scheduled visit) is average of binge eating days on the mapped Week 7 and/or binge eating days on the mapped Week 8. The derived binge eating days per week at Week 1, 2, 3, 4, 6 and 8 (scheduled visits) will be included in MMRM model for primary efficacy analyses.

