8.3 Key Secondary Efficacy Endpoint

The key secondary endpoint is change from baseline in CGI-S score at Week 8. CGI-S assessment collected at scheduled visits will be mapped to the weeks per specification in Table 5.2-2. This key secondary efficacy endpoint will be analyzed by fitting the MMRM model with treatment group, trial center, visit week, and an interaction term of treatment by visit week as fixed effect terms, and interaction term of baseline value by week as covariates. The similar approach of selection of covariance matrix for MMRM model will be applied as for primary efficacy endpoint.

Sensitivity analyses for the key secondary endpoint will be performed as specification in Section 8.2.2.1 as needed.

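### If the unstructured MMRM does not converge, the plan goes straight to structured covariances that can bias the Weeks 7-8 difference under MAR; it should first try to keep the unstructured matrix (low priority, no cost)

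*Protocol*

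**What the plan says.** The primary model is an MMRM on change in binge eating days per week with an unstructured covariance (Protocol 1.1 and 9.4.1.1; SAP 8.2.1). On its visits, Protocol 9.4.1.1 states: "The level of visit in the MMRM will include Week 1, Week 2, Week 3, Week 4, Week 6, and Week 8". The six values are not built alike. Weeks 1 to 4 are single-week values, but under SAP 8.2.3.1 "Binge eating days per week for week 6 (scheduled visit) is average of binge eating days on the mapped Week 5" and Week 6, and the Week 8 value likewise combines mapped Weeks 7 and 8.

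If the unstructured fit has a convergence problem, "the following structures other than unstructured will be used in order of 1) heterogeneous toeplitz, 2) heterogeneous autoregressive of order 1", followed by heterogeneous compound symmetry. With any of these the plan adds a sandwich variance, described in these words: "estimator of the standard error of the fixed effects parameters will be used in order to deal with possible model misspecification". The code in SAP 8.2.3.3 shows only TYPE=UN with Kenward-Roger degrees of freedom. No step between TYPE=UN and the structured list appears in the visible text.

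The estimand is hypothetical, and withdrawal from treatment is handled as missing at random through the MMRM (Protocol 9.3 and 9.4.1.1). The key secondary endpoint, CGI-S, inherits the rule: "The similar approach of selection of covariance matrix for MMRM model will be applied as for primary efficacy endpoint" (SAP 8.3).

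**The concern.** When subjects drop out, an MMRM in effect predicts each missing Week 8 value from that subject's earlier visits, and the fitted covariance sets the weights. An unstructured matrix lets the data choose them. A structured matrix imposes them: AR(1) predicts from the last observed visit alone, compound symmetry gives every pair of visits the same correlation, and Toeplitz lets correlation depend only on how many visits apart two values are. None of these need fit a series of four single-week values followed by two two-week averages.

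If the weights are wrong, the predicted means of dropouts are wrong, and a sandwich standard error does not move them. At stake is the validity of the primary estimate under the plan's own MAR assumption. If the fallback were used, the result would partly depend on which structure happened to converge.

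**Working it through.** **1. The plan's own figure.** Protocol 9.1 has "Assuming a treatment difference of 1.1 points with a standard deviation of 1.7" and 38 evaluable subjects per arm. SE of the difference = 1.7 × √(2/38) = 0.390. Power = Φ(1.1/0.390 − 1.96) = Φ(0.86) = 0.805, so at least 80% is reproduced (0.795 with the noncentral t). Implied loss = (126 − 114)/126 = 12/126 = 9.5%.

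**2. Size of the unstructured matrix.** Six visits give 6 × 7/2 = 21 covariance parameters, estimated from about 126 subjects.

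**3. Why the sandwich does not help the estimate.** For a working covariance V, the estimate is b = (X′V⁻¹X)⁻¹X′V⁻¹y. The sandwich replaces the variance formula for b and leaves b itself unchanged. A subject last seen at visit k contributes a predicted Week 8 value of μ₈ + V₈ₖVₖₖ⁻¹(y − μ) over the observed visits. If V is wrong, an arm's Week 8 mean shifts by roughly (dropout share) × (error in weights) × (how far dropouts sit from their arm's mean). The treatment difference carries the difference of the two shifts, so equal shifts cancel.

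**4. Large-sample check.** Each setting used 400,000 subjects per arm, visit values built as in SAP 8.2.3.1, a Weeks 7-8 SD of 1.7, a true difference of −1.1, and dropout depending on the last observed value.

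Assumptions that are not in the documents:
- Four true correlation patterns: exponential decay; random intercept plus decay plus noise; random intercept plus noise; random intercept and slope.
- Dropout of 9.5% or 25% in each arm.
- Dropout log-odds slopes per SD (placebo/active) of 1/1, 1/0 or 1/−1.

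Bias is the estimate minus −1.1; positive understates benefit. Ranges cover the four patterns when the dropout mechanism differs by arm:

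| Structure | 9.5% dropout | 25% dropout |
|---|---|---|
| Unstructured | within ±0.006 | within ±0.006 |
| Toeplitz | −0.023 to +0.044 | −0.065 to +0.126 |
| AR(1) | −0.031 to +0.116 | −0.083 to +0.327 |
| Compound symmetry | −0.081 to +0.028 | −0.226 to +0.082 |

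Repeat runs put the largest AR(1) value at 9.5% slightly higher, at about 0.13. With the same mechanism in both arms (1/1), the bias was about 0 for every structure.

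The range ends come from the 1/−1 setting, in which worse placebo subjects and better active subjects leave. In a repeat with outcome-related dropout on placebo only (1/0), the 9.5% ranges shrink to −0.014 to +0.019 (Toeplitz), −0.017 to +0.059 (AR(1)) and −0.039 to +0.011 (compound symmetry).

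**5. Scale at 9.5% dropout.**
- Toeplitz: 0.044/0.390 = 0.11 SE, and 0.044/1.1 = 4% of the planned difference.
- AR(1): 0.13/0.390 = 0.33 SE, or 12% of 1.1. Power would be Φ((1.1 − 0.13)/0.390 − 1.96) = Φ(0.53) = 0.70 instead of 0.805.
- Compound symmetry: 0.081/0.390 = 0.21 SE, in the direction that overstates benefit. The two-sided error would be about 5.5% instead of 5%.

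At 25% the worst cases are 0.32 SE (Toeplitz), 0.84 SE (AR(1)) and 0.58 SE (compound symmetry, error about 8.9%).

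**The case against.** **The trigger is remote.** This stands. The fallback applies only if the unstructured fit fails, and neither document gives a failure rate. In 200 simulated trials of 126 subjects the unstructured estimate stayed well conditioned. Toeplitz comes first and is nearly harmless at 9.5%; material bias mostly needs Toeplitz to fail too.

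**Differential dropout is an assumption.** This also stands. Protocol 4.3 reports dose-dependent side effects, and Protocol 7.3.3 lists adverse events, rash and lack of efficacy among the reasons for stopping. Tolerability dropout on drug with efficacy dropout on placebo is therefore plausible, but the documents do not establish it.

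**Other analyses would show a distortion.** This stands in part. SAP 5.3.1 names model-based imputation and pattern-mixture models, and SAP 8.2.2.3 adds weighted GEE and multiple imputation with robust regression. Some of the sensitivity text is withheld. These analyses are supportive and do not replace the primary estimate.

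**A reader might infer that unequal spacing is the fault and that a time-based structure would cure it.** The evidence does not support this. Toeplitz and AR(1) do work on visit order, but compound symmetry uses no spacing at all. AR(1) bias at 9.5% was only −0.02 to −0.03 under pure exponential decay, where spacing matters most, and +0.06 to +0.12 under random intercept plus noise, where spacing is irrelevant. A heterogeneous spatial power structure in real time nearly removed the bias under exponential decay (at most 0.013) but was worse than Toeplitz and AR(1) in the other three patterns.

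**A reader might also infer that the plan claims the sandwich repairs the estimate.** It does not; the text refers to the standard error. The gap is only that nothing addresses the estimate.

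**Conclusion.** The point holds as a low-priority improvement. The structured fallbacks can be misspecified for these visits, the sandwich does not protect the estimate, and the visible plan makes no attempt to keep the one covariance that was unbiased in every setting checked.

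At the implied 9.5% dropout the bias is at most about 0.04 days per week for Toeplitz, 0.13 for AR(1) and 0.08 for compound symmetry. At 25% it reaches about 0.3 for AR(1). It can favor or disfavor the drug. All sizes rest on assumed correlations and dropout models, and on reading the 9.5% non-evaluable share as dropout.

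It would be too strong to say that the primary and key secondary estimates lose validity whenever the fallback is used: the bias also needs outcome-related dropout that differs by arm. CGI-S was not modelled, so for that endpoint only the shared rule is established, not a size.

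**What to change.** In Protocol 1.1 and 9.4.1.1 and SAP 8.2.1 (SAP 8.3 follows by reference), insert a step before the structured list:

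- If TYPE=UN does not converge, refit the same unstructured covariance as TYPE=FA0(6) or TYPE=UNR, and/or with PARMS starting values from the Toeplitz fit, keeping Kenward-Roger.
- Use the listed structures, in the listed order, only if these refits also fail.
- State that with a structured matrix the sandwich estimator protects the standard error and not the point estimate.

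No spacing-based replacement structure is recommended. The cost is a sentence or two of wording and a few lines of SAS, settled before unblinding. It needs no extra data or subjects, and results are unchanged if the first unstructured fit converges.
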